### 7.7.2 Arterial Access

Standard methods are used to gain access to the femoral artery. Standard methods are used (e.g., sheaths and guide catheters) to obtain access to the IA. Tri-axial approach, although not mandatory, is highly recommended.

### 7.7.3 Angiogram

A cerebral angiogram of the target IA and the parent artery at the beginning of the procedure will be performed to confirm final eligibility for the study.

 Described at: [http://www.ninds.nih.gov/doctors/nih\\_stroke\\_scale.pdf](http://www.ninds.nih.gov/doctors/nih_stroke_scale.pdf)

	Document Number	Rev F	Page 13 of 34
	DNX065-01		
Design History Document	Title		
Confidential & Proprietary	Clinical Investigation Plan, Contour Neurovascular System™		

#### 7.7.4 Contour Neurovascular System™ Placement

Contour Neurovascular System™ placement is described in detail in the Instructions for Use. Briefly, the target IA is accessed via standard methods. A 0.027” microcatheter is placed into the target IA. The Contour Neurovascular System™ device is introduced into the microcatheter and slowly delivered into the target IA. Once the Contour implant is in the appropriate location, the device is detached via a standard electrolytic mechanism.

A final post-placement angiogram, which includes a 3D angiogram of the aneurysm and parent vessel, will be performed and all devices are removed from the body. All relevant radiographic images should be saved. Specifically, the investigator should document flow disruption compared to pre-placement flow. Any device deficiencies, technical complications or adverse events occurring during the procedure should be noted in the CRF.

All images captured during the procedure, including the 3D angiogram, are to be submitted to the independent core laboratory.

Peri-operative anti platelet use is not excluded and may be used at the discretion of the operator.

#### 7.8 Hospital Discharge

The subject will be discharged from the hospital as per standard practices. Prior to discharge, the investigator should evaluate the subject for any adverse events and perform a neurologic examination.

#### 7.9 Follow-Up

The subject will have a follow-up visit at six (6) weeks, six (6) months, and one (1), two (2), three (3), four (4) and five (5) years after the study procedure. At each study visit, the subject should be assessed for any new adverse events. A standard neurologic examination should be performed to evaluate for any new adverse events. A modified Rankin Scale (mRS) will be recorded at each follow-up visit. It is expected that most target IAs will be asymptomatic and the likelihood of post-placement neurologic changes is very low. The NIH Stroke Scale is recorded if a stroke has occurred.

Cerebral angiography will be repeated at six (6) months and one (1) year. At six (6) months, the cerebral angiography will include a 3D angiogram, and at one (1) year the angiogram will include the conventional AP, lateral and working projections. The investigator should ensure that follow-up angiography is done with identical views to maximize the ability to compare baseline and post-treatment views. All angiographic images should be submitted to the independent core laboratory. The target IA status will be evaluated by an independent core laboratory using an appropriate aneurysm scoring scale(s) such as the Raymond Scale and/ or the Web Occlusion Scale (WOS).

An MRI/MR angiogram (TOF & Contrast enhanced MRA) will be performed in all subjects at 6 months follow up. The purpose of the MR is to establish and compare the MR and angiographic appearances of the target IA.

If the cerebral angiogram shows complete occlusion at both the 6-month and 1-year time frames, the investigator may choose alternative methods for the 2, 3, 4 and 5-year angiography (e.g., MRI/MRA). If the cerebral angiogram at either 6 months or 1 year shows incomplete target IA occlusion, the 2, 3, 4 and 5-year exam should include a standard cerebral angiogram.

The subject’s participation in the study is complete after the 5-year visit and angiogram/MR are completed.

	Document Number	Rev F	Page 14 of 34
	DNX065-01		
Design History Document	Title		
Confidential & Proprietary	Clinical Investigation Plan, Contour Neurovascular System™		

The study's schedule of assessments and allowed post-treatment visit windows are shown in **Table 3** below.

**Table 3. Schedule of assessments**

	Baseline	Procedure	Discharge	weeks ± weeks	months ± month	Year 1 (± month)	Year 2, 3, 4, 5 (± month)
Medical history and medications	X						
Neurologic exam	X		X	X	X	X	X
NIH Stroke Scale	X		X*	X*	X*	X*	X*
Modified Rankin Scale (mRS)	X		X	X	X	X	X
Pregnancy test (pre-menopausal female)	X						
Cerebral angiogram	X** w/3D	X w/3D			X w/3D	X	X§
Adverse events		X	X	X	X	X	X
Procedure information		X					
Aneurysm scoring scale		X			X	X	X#
MRI/MRA					X		X§

\*The NIH Stroke Scale score should be obtained within 7 days after stroke in the event a subject is diagnosed with a stroke

\*\*Baseline cerebral angiogram with 3D can be completed within 3 months of enrolment

# Aneurysm scoring scale completed when cerebral angiograms are performed

§MRA/Cerebral Angiogram Optional: If the cerebral angiogram shows complete occlusion at both the 6month and 1-year time frames, the investigator may choose alternative methods for the 2, 3, 4 and 5-year angiography (e.g., MRI/MRA).

## 7.10 Early Withdrawal

Reasons for subject withdrawal prior to study completion will be documented on the CRF. Valid reasons for early study withdrawal include:

- Death
- Adverse event or other medical condition that prevents study participation
- Withdrawal of voluntary consent
- Loss to follow-up

 Cerus Endovascular	Document Number	Rev F	Page 15 of 34
	DNX065-01		
Design History Document	Title		
Confidential & Proprietary	Clinical Investigation Plan, Contour Neurovascular System™		

- Study is terminated

At least three documented attempts will be made to contact any subject who is lost to follow-up. If the study is terminated for any reason, the governing Ethics Committee will be notified.

## 7.11 Variables

### 7.11.1 Primary Variables

The primary variables are safety as this is a pilot study.

The safety variables to be collected and reported are the occurrence and frequency of AEs, ADEs, SAEs, SADEs and USADEs.

Specific AEs associated with this procedure that shall be evaluated include but are not limited to: blood vessel perforation or rupture, unintended thrombosis, adverse tissue reaction, infection, and hematoma formation, and major ipsilateral stroke/ SAH or death due to neurologic cause within 6 months after treatment.

### 7.11.2 Secondary Variables

Secondary variables to be collected and reported in order to aid in the design of future studies are listed below.

**Efficacy:** Efficacy variables are related to the ability of the device to embolize the aneurysm and shall be analyzed relative to the baseline visit. The variables to be collected and reported shall include but are not limited to:

Angiographic and/or MRI/ MRA assessment of aneurysm occlusion including evaluation of occlusion grade, parent vessel patency, physical positioning, occlusion durability, and any device migration.

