Currently, the most commonly provided endovascular therapy for IAs is coil embolization. Despite the high prevalence of its use, coil embolization is substantially restricted due to geometric limitations and target IA access. Moreover, complete occlusion of the target IA is relatively uncommon; in a large randomized trial of coil embolization, complete occlusion of the target IA at 6-month follow-up was seen in only about 30% of cases.

It is commonly accepted that large IAs or those with a neck size >4 mm are more difficult to completely occlude with embolization coils. Wide-necked IAs are especially difficult to treat, as the geometry of the IA does not allow coils to stay in place. Adjunctive devices to improve coil embolization in wide-necked IAs are available. Balloon catheters may aid the clinician in packing the IA with coils and several intravascular stents are now commercially available. These stents are placed in the parent artery adjacent to the target IA; stent struts help to hold coils in place inside the target IA. Unfortunately, few studies are available to estimate the relative increase in complete occlusion rate provided by these adjunctive devices. Even more challenging is the treatment of wide-necked IAs located at arterial bifurcations. Placement of intracranial stents in a variety of configurations has been associated with a significantly higher risk.

Incomplete occlusion has additional risks, including growth of the IA and reopening related to continued pulsatile blood flow into the IA. Moreover, coils can become compacted and regress into the dome of the IA, resulting in further filling at the IA neck. In addition to exposing patients to bleeding risk, incomplete IA occlusion is also associated with the need for surveillance, which is stressful for patients. More importantly, these patients may need another embolization. Retreatment procedures can be complex and not always successful, thereby exposing the patient to further risk.

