**Table 4. Adverse event definitions per ISO 14155:2011**

Adverse event	
An Adverse Event (AE) is:  “any untoward medical occurrence, unintended disease or injury, or untoward clinical signs (including abnormal laboratory findings) in subjects, users or other persons, whether or not related to the investigational medical device.  Note 1: This definition includes events related to the investigational medical device or the comparator.  Note 2: This definition includes events related to the procedures involved.  Note 3: For users or other persons, this definition is restricted to events related to investigational medical devices.”

Adverse device effect	
An Adverse Device Effect (ADE) is:  “adverse event related to the use of an investigational medical device.”  Note 1: This definition includes events resulting from insufficient or inadequate instructions for use, deployment, implantation, installation, or operation, or any malfunction of the medical device.  Note 2: This definition includes any event resulting from use error or from intentional misuse of the investigational medical device.

Serious adverse event	
A Serious Adverse Event (SAE) is:  “an adverse event that
 
 
• led to death,
 
• led to serious deterioration in the health of the subject that either resulted in 
 
○ a life-threatening illness or injury, or
 
○ a permanent impairment of a body structure or a body function, or
 
○ in-patient or prolongation hospitalization, or
 
○ medical or surgical intervention to prevent life-threatening illness or injury or permanent impairment to body structure or body function,
 
 
 
• led to foetal distress, foetal death, or a congenital abnormality, or birth defect.” Note: Planned hospitalization for a pre-existing condition, or a procedure required by the clinical investigational plan, without serious deterioration in health, is not considered to be a serious adverse event.
 

Serious adverse device effect	
A Serious Adverse Device Effect (SADE) is:  “adverse device effect that has resulted in any of the consequences characteristic of a serious adverse event.”

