## 9.1 General Principles

This is a pilot study intended to collect and report data on the use of the Contour Neurovascular System™.

The primary analysis for all baseline characteristics and study variables will include all available data for all enrolled subjects. Standard summary statistics will be calculated for all study variables. For continuous variables, statistics will include means, standard deviations, medians and ranges. Categorical variables will be summarized in frequency distributions.

Statistical analyses will be conducted in SAS version 9.3 or above (SAS Institute, Cary, N.C.), R version 3.2 or above (R Core Team, <http://www.R-project.org>) or another validated statistical software package.

For adverse event reporting, the primary analysis will be based on subject counts, not event counts. Both subject counts and event counts will be presented in tabular summaries of results.

As this is a pilot study, formal hypothesis testing of the study variables will not be performed and multiple testing procedures are not incorporated in the statistical analysis.

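### Retreatment of the target aneurysm is foreseen but never scheduled for recording, and no rule covers occlusion grades obtained after it

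*Combined protocol and SAP*

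**What the plan says.** The Introduction (section 4) discusses what follows incomplete occlusion: "More importantly, these patients may need another embolization". It adds that such procedures carry further risk and can fail. This is the only place where retreatment is named.

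Section 7.11.2 states the purpose of the secondary variables: "Efficacy variables are related to the ability of the device to embolize the aneurysm". The list that follows covers "evaluation of occlusion grade, parent vessel patency, physical positioning, occlusion durability, and any device migration". It is open-ended ("The variables to be collected and reported shall include but are not limited to"), but no further item is named anywhere.

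Section 9.1 sets the analysis rule: "The primary analysis for all baseline characteristics and study variables will include all available data for all enrolled subjects". It makes no exception for observations that follow a second treatment.

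Section 7.9 calls for cerebral angiography at 6 months and 1 year. If either shows incomplete occlusion, conventional angiography should continue at years 2 to 5. A footnote to Table 3 has the aneurysm scoring scale completed whenever an angiogram is done. Table 3 schedules procedure information only at the index procedure, and history and medications only at baseline. Section 7.10 does not list retreatment as a reason for withdrawal.

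**The concern.** The question is a second intervention on the target aneurysm months or years after the index procedure. Take a subject who is incomplete at 6 months, is coiled at month 8, and is graded complete at 1 year. Nothing in the plan separates that grade from one produced by the Contour implant alone, and no scheduled data item would let the analyst separate it afterwards.

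The subjects most likely to be retreated are those with incomplete occlusion, and they are also the ones whose later angiography and scoring are most firmly scheduled. If the default is followed, some device failures appear as complete occlusion in the later summaries. Section 7.11.2 says the secondary variables are meant to help design future studies, so an inflated late occlusion rate could carry into the assumptions of the next trial.

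**Working it through.** **The plan's own figure.** The only statistical figure is the standard error of 4.5% to 5.4% for the primary safety variable (section 9.4). No event rate is stated. With SE = √(p(1−p)/n) and an assumed p = 0.10, the result is 4.47% at n = 45 and 5.48% at n = 30: close to the stated figures, but not testable without p. The present point does not depend on it.

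**Reading the sections together.**
1. 7.11.2: efficacy is about what the device does.
2. 7.9 and Table 3: an incompletely occluded aneurysm continues to be imaged and scored to year 5.
3. 7.10: a retreated subject stays in the study. That is helpful, because the follow-up is needed.
4. Table 3: no follow-up item asks about re-intervention.
5. 9.1: all later observations are used, with no stated exception.

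Steps 2 to 5 put a post-retreatment grade into the occlusion summary by default. That does not match step 1.

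**Size.** The documents give no occlusion rate, retreatment rate or retreatment success rate. All counts below are assumptions.

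*Per subject.* One retreated-then-occluded subject adds 1/N: 1/45 = 2.2 points at the maximum enrolment, 1/30 = 3.3 points at the minimum evaluable number in 9.4.

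*Worked case.* Suppose N = 40, with 24 complete without retreatment.
- Device rate: 24/40 = 60%.
- SE = √(0.6 × 0.4/40) = 7.7 points.
- Four retreated, half then complete: 26/40 = 65%, an excess of 5 points, or 5/7.7 = 0.65 SE.
- Four retreated, all then complete: 28/40 = 70%, an excess of 10 points, or 10/7.7 = 1.3 SE.

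*Range.* With about 5% to 15% of subjects retreated and 50% to 100% of those then occluded (rounded to whole subjects), the excess runs from 1/45 = 2.2 to 7/45 = 15.6 points at N = 45, and from 1/30 = 3.3 to 4/30 = 13.3 points at N = 30.

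*Exclusion is not neutral.* Suppose N = 45, with 27 occluded by the device alone and 4 retreated, all then occluded.

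| Handling | Complete occlusion |
|---|---|
| Default under 9.1 | 31/45 = 68.9% |
| Retreatment counted as not occluded by the device | 27/45 = 60.0% |
| Retreated subjects excluded | 27/41 = 65.9% |

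Dropping retreated subjects also raises the rate, because it removes known failures from the denominator.

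**The case against.** **No sentence credits a later treatment to the device.** A reader might infer that the plan deliberately counts a retreated aneurysm as a Contour success. It does not say so: 9.1 is a general statement about which data are analysed, and 7.11.2 points the other way. What stands against the plan is narrower: handling is unspecified, and the default conflicts with the stated purpose.

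**The list is open and a guidance document is promised.** Section 7.11.3 has an imaging guidance document prepared before core-laboratory analysis begins. It could contain a rule, but nothing here promises one, and a guide to reading images would not ordinarily create a CRF item.

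**Durability.** A reader might infer that durability is also biased upward. Durability is not defined, so this cannot be shown. A subject who was never completely occluded had no occlusion to endure.

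**Safety capture.** A reader might infer that retreatments escape safety reporting, because the SAE note in Table 4 says: "Planned hospitalization for a pre-existing condition, or a procedure required by the clinical investigational plan, without serious deterioration in health, is not considered" a serious adverse event. The documents do not support that. The note bears on SAE status only, and AEs are still assessed at every visit. The independent Medical Monitor reviews all AEs (8.2) and the sponsor classifies them (11.2.12). Recanalization and migration causing incomplete occlusion are listed device risks (6.1), so calling a retreatment for either of them care of a pre-existing condition is strained. What remains is that an AE record, even a complete one, is not linked to the occlusion summary.

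**Choice of estimand and status.** Occlusion regardless of retreatment is a legitimate quantity too, so both should be shown. The outcomes are secondary and descriptive, and "formal hypothesis testing of the study variables will not be performed". That limits the severity but does not remove the attribution problem.

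**Conclusion.** The concern holds as an omission with a predictable default. Retreatment is foreseen, is not scheduled for recording, and has no analysis rule. Following 9.1 as written places post-retreatment grades in the 1- to 5-year occlusion summaries, which can overstate occlusion by the device.

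The size is 2.2 points (N = 45) to 3.3 points (N = 30) per retreated-then-occluded subject. In the N = 40 case, four retreatments give 5 to 10 points, or 0.65 to 1.3 standard errors. These figures rest wholly on assumed counts, and the effect is zero if nobody is retreated or if no retreatment succeeds. The effect on durability depends on a definition the plan does not give. The primary safety analysis and the sample size are unaffected. The change should be made, but the study does not stand or fall on it.

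**What to change.** - **Table 3 and CRF:** add a target-aneurysm retreatment item at each follow-up visit (yes/no, date, reason, device used).
- **Section 7.11.2:** list the retreatment rate, with all subjects who had a device placed as the denominator.
- **Section 9.1:** state that, for occlusion by the device, a subject counts as not completely occluded from the date of retreatment. Show the as-observed grade beside it.
- **Enrolment scenario 4 (section 7.5):** an additional endovascular device at the index procedure raises the same attribution problem, so show these subjects as a separate line.
- **Safety reporting:** list retreatments separately and flag AEs that start on or after retreatment. The safety variables in 7.11.1 and the definitions in Table 4 can stay as they are.

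The cost is a CRF update, short text in 7.11.2 and 9.1, some extra table lines and a listing, and a CIP amendment with ethics committee approval. No extra visits, imaging or subjects are needed. The downside is that later occlusion figures become somewhat less favourable. The change concerns recording and analysis only; no rule on when to retreat is proposed.

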### 7.11.3 Independent Analysis of Imaging

Follow-up imaging (i.e., cerebral angiograms and/or MRI/MRA) will be evaluated and angiographic assessments of the aneurysm will be completed by an independent core laboratory with experience in neurovascular imaging of IAs. Clinicians responsible for imaging analyses at the core laboratory will not have any financial conflict with the study sponsor and will not be affiliated with a clinical study site. An imaging guidance document will be prepared before analysis begins at the independent core laboratory.

## 8 Adverse Events

Definitions of adverse event subtypes are provided in Table 4 below. The occurrence of all adverse events will be reported by the clinical site investigator on a specific case report form (CRF).

NOTE: As detailed in section 8.3, the reporting of AEs shall follow MEDDEV 2.7/3, 2015 and shall not make any difference between anticipated and unanticipated AEs.

**Table 4. Adverse event definitions per ISO 14155:2011**

Adverse event	
An Adverse Event (AE) is:  “any untoward medical occurrence, unintended disease or injury, or untoward clinical signs (including abnormal laboratory findings) in subjects, users or other persons, whether or not related to the investigational medical device.  Note 1: This definition includes events related to the investigational medical device or the comparator.  Note 2: This definition includes events related to the procedures involved.  Note 3: For users or other persons, this definition is restricted to events related to investigational medical devices.”

Adverse device effect	
An Adverse Device Effect (ADE) is:  “adverse event related to the use of an investigational medical device.”  Note 1: This definition includes events resulting from insufficient or inadequate instructions for use, deployment, implantation, installation, or operation, or any malfunction of the medical device.  Note 2: This definition includes any event resulting from use error or from intentional misuse of the investigational medical device.

Serious adverse event	
A Serious Adverse Event (SAE) is:  “an adverse event that
 
 
• led to death,
 
• led to serious deterioration in the health of the subject that either resulted in 
 
○ a life-threatening illness or injury, or
 
○ a permanent impairment of a body structure or a body function, or
 
○ in-patient or prolongation hospitalization, or
 
○ medical or surgical intervention to prevent life-threatening illness or injury or permanent impairment to body structure or body function,
 
 
 
• led to foetal distress, foetal death, or a congenital abnormality, or birth defect.” Note: Planned hospitalization for a pre-existing condition, or a procedure required by the clinical investigational plan, without serious deterioration in health, is not considered to be a serious adverse event.
 

Serious adverse device effect	
A Serious Adverse Device Effect (SADE) is:  “adverse device effect that has resulted in any of the consequences characteristic of a serious adverse event.”

Unanticipated serious adverse device effect	
An Unanticipated Serious Adverse Device Effect (USADE) is:  “a serious adverse device effect which by its nature, incidence, severity or outcome has not been identified in the current version of the risk analysis report.”  Note: Anticipated serious adverse device effect (ASADE) is an effect which by its nature, incidence, severity or outcome has been identified in the risk analysis report.

